**The Impact of Serial Remote Ischemic Conditioning on Dynamic
Cerebral Autoregulation in Healthy Adults**

The First Hospital of Jilin University

NCT 04899362

April 10th, 2021

Background

Remote ischemic conditioning (RIC) refers to an intervention that offers remote tissues and organs a resistance capacity to ischemia/reperfusion injury through small doses of reversible episodes of ischemia and reperfusion that activate neurogenic pathways, humoral factors, and the immune system. Recent studies have demonstrated that RIC could increase cerebral perfusion, promote hematoma resolution, facilitate recovery of nerve function, and improve the clinical prognosis of patients with cerebrovascular diseases. However, the mechanism is not fully elucidated. Our previous study found that dynamic cerebral autoregulation (dCA), an important indicator of cerebrovascular function which related to the prognosis of cerebrovascular disease, was improved after once round of RIC; however, the exact effect of serial RIC on dCA was unclear. Additionally, the dCA alteration period after serial RIC remains unknown. Solving these problems will help us to formulate detailed strategies for the safe and effective application of RIC in patients with cerebrovascular disease.

Hence, the objective of this study was to observe the exact impact of serial RIC on dCA. This included determining when dCA was increased during serial RIC and the duration of the effect of serial RIC.

Eligibility Criteria

Inclusion Criteria:

- age from 18 to 50, both genders
- willing to participate in follow-up visits

Exclusion Criteria:

- current or having a history of chronic physical diseases or mental diseases
- suffering from infectious diseases in late one month
- pregnant and lactating women
- smoking or drinking
- inability to cooperate sufficiently to complete the dCA examination

Arms and Interventions

Experimental: RIC group

RIC was induced by 4 cycles of extremities ischemia (5-minute blood-pressure cuff inflation to 200 mm Hg, followed by 5-minute cuff deflation). All subjects will take 14 RIC intervention, blood collection and 10 dCA measurements.

Device: BB-RIC-D1/LAPUL Medical Devices Co, Ltd, China

The RIC consisted of 4 cycles of extremities ischemia (5-minute blood pressure cuff inflation to 200 mm Hg, followed by 5-minute cuff deflation). The tourniquets were applied to one side upper arm. This intervention was undertaken twice a day for 7 days.

Procedure/Surgery: Intravenous blood collection

Nurses will collect intravenous blood 3ml four times (at baseline and the first, seventh and eighth day of the study). The blood samples will be stored for laboratory test. The blood samples only use for the trial.

Device: dCA measurement

Serial measurements of dCA were performed at 10 days, baseline, 1st, 2nd, 4th, 7th, 8th, 10th, 14th, 21st and 35th of the study. The continuous ABP was measured non-invasively using a servo-controlled plethysmograph (Finometer Pro, the Netherlands) at the middle finger. Two 2 MHz transcranial Doppler probe was used to measure continuous cerebral blood flow velocity (CBFV) simultaneously in the bilateral middle cerebral arteries at a depth of 45-60 mm. Endtidal CO₂ was monitored using a capnograph (MultiDop X2, DWL, Sipplingen, Germany). The probes were placed over temporal windows and fixed with a customized head frame. CBFV and continuous arterial blood pressure were recorded simultaneously from each subject in the supine position for 10 minutes. All data were recorded for further assessment and analysis.

Outcome Measures

Primary Outcome Measure:

Dynamic Cerebral Autoregulation Parameter: Phase Difference(PD) in Degree
[Time Frame: 36 days]

Low PD at a low frequency band indicates impairment of autoregulation, as it suggests that cerebral blood flow velocity follows the changes in arterial blood pressure with a short delay.

Secondary Outcome Measures:

Dynamic Cerebral Autoregulation Parameter: Gain in cm/s/mmHg [Time Frame: 36 days]

High gain at the same frequency band is also considered an indicator of compromised autoregulation for passively transferring the amplitude of arterial blood pressure to cerebral blood flow velocity.

Statistical Analysis Plan

The data were analyzed using the Statistical Program for Social Sciences version 26.0 (SPSS; IBM, West Grove, PA). The distribution of data was assessed using a one-sample Kolmogorov–Smirnov test. Normally distributed continuous variables are shown as mean \pm standard deviation, and non-normally distributed data are presented as the median and interquartile range. Repeated measurement analysis of variance was used to test the differences in the observed dCA values on different days. Two general linear models were used for the repeated measurements. To observe when dCA was increased during serial RIC, dCA parameters at baseline, d1, d2, d4, and d7 were included. To assess the duration of the effect of serial RIC, baseline, d7, d8, d10, d14, d21, and d35 were included. To compare the difference between the baseline and other days, a paired t-test was used. The changes in blood biomarker levels were analyzed by Friedman test. Baseline, d1 and d7, and baseline, d7 and d8 were compared respectively. A two-tailed p-value < 0.05 was considered statistically significant.

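### The overall test in the duration model can be significant from day 7 versus baseline alone, so it does not show that the effect outlasts treatment

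*Combined protocol and SAP*

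**What the plan says.** The objective in the Background section has two parts: "determining when dCA was increased during serial RIC and the duration of the effect of serial RIC". The Statistical Analysis Plan gives each part its own repeated-measures model ("Two general linear models were used for the repeated measurements").

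- Onset: "To observe when dCA was increased during serial RIC, dCA parameters at baseline, d1, d2, d4, and d7 were included".
- Duration: "To assess the duration of the effect of serial RIC, baseline, d7, d8, d10, d14, d21, and d35 were included".

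Day-specific comparisons follow: "To compare the difference between the baseline and other days, a paired t-test was used". The only threshold is "A two-tailed p-value < 0.05 was considered statistically significant". No multiplicity adjustment is given, and nothing is said about checking or correcting for sphericity.

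On the intervention, Arms and Interventions says "This intervention was undertaken twice a day for 7 days". Day 7 therefore belongs to the treatment period, and the onset sentence itself lists it among the days during treatment. Day 8 is the first measurement after treatment.

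**The concern.** Baseline and day 7 are in both models. Their difference is the end-of-treatment effect, which the onset model already tests. With both days in the duration model, an end-of-treatment effect is enough to make its null hypothesis false, whatever happens from day 8 on. A significant result cannot separate an effect that lasts from one that stopped with treatment.

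Duration is one of the two stated aims, and this is the model that the plan names for it. The paired t-tests are the other route to a duration statement. There are five of them after treatment, each judged at 0.05 as far as the plan says, so that route has an error rate well above 5% when nothing persists.

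**Working it through.** The documents contain no sample size, power, SD, effect size or correlation, so there is no planned figure to reproduce. The model structure comes from the Statistical Analysis Plan. The values of n, d and correlation are assumptions.

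**1. Null hypothesis of the duration model.** Seven means are equal: baseline, d7, d8, d10, d14, d21, d35. Suppose day 7 is shifted by d, in SDs of PD across subjects on one day, and every other day equals baseline. The null is then false although nothing persists. This follows from the design and needs no simulation.

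**2. How often the overall test is significant in that case.** With equal correlation rho between days, F has 6 and 6(n-1) degrees of freedom and noncentrality

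lambda = n × d² × (1 - 1/7) / (1 - rho).

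Example with n = 30, d = 0.5, rho = 0.5: lambda = 30 × 0.25 × 0.857 / 0.5 = 12.86. The 5% critical value of F(6, 174) is 2.15, which gives 76%. Other cases at rho = 0.5:

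| n | d = 0.3 | d = 0.5 | d = 0.7 |
|---|---|---|---|
| 10 | 11% | 26% | 50% |
| 20 | 20% | 54% | 87% |
| 30 | 30% | 76% | 98% |
| 50 | 50% | 95% | about 100% |

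Simulation under three assumed covariance patterns, with n = 20 to 50 and d = 0.5 to 0.7, gives about 47-100%.

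**3. Which change removes the problem.** Greenhouse-Geisser with day 7 kept barely helps: at n = 30, d = 0.5, rho = 0.5 the rate is 72% instead of 76%. Removing day 7 brings it to 4-6% at rho = 0.5 without any correction, and to 4-5% with Greenhouse-Geisser under the three patterns. Day 7 is the cause.

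**4. Paired t-tests when the effect is gone by day 8.** There are five post-treatment tests: d8, d10, d14, d21, d35. If they were independent, the chance of at least one false positive would be 1 - 0.95⁵ = 22.6%. They share the baseline value, so the chance is lower: about 16-19% in simulation. If they were read only after a significant overall test, a rule that the plan does not state, the rate would be 14-18% with day 7 in the model and about 3-4% with day 7 out. Holm starts at 0.05 / 5 = 0.01 and gives about 4-5% for the family.

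**5. Sphericity.** With baseline as day 0, the gaps in the duration model are 7, 1, 2, 4, 7 and 14 days, so equal correlation between days is doubtful. With no change over time, the uncorrected duration test rejects about 5% when sphericity holds and up to about 8% under serial correlation (epsilon about 0.66). With Greenhouse-Geisser it rejects at most 5% in every pattern tried.

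**6. What the overall test shows once day 7 is out.** Put the shift on day 8 only, with six levels: lambda = 30 × 0.25 × (1 - 1/6) / 0.5 = 12.5, with 5 and 145 degrees of freedom, which gives 77%. The test then shows that some post-treatment day differs, not how long the effect lasts.

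**The case against.** The strongest reply is that the plan already answers duration day by day. The paired t-tests compare baseline with each later day, and nothing in the plan says that a significant overall test will be read as persistence. That is right, and it limits the harm. It does not remove it: the plan assigns the duration aim to the model, does not say that the conclusion rests on the t-tests, and states no adjustment for them.

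A second reply is that the end-of-treatment level is the natural starting point for a decay, and that dropping day 7 only passes the same weakness to day 8 (step 6). The first half is fair, which is why day 7 versus later days should stay as named contrasts. The second half stands as a limit of any overall test. The cases still differ, because a day 8 difference is a post-treatment effect and a day 7 difference is not.

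Four stronger readings are tempting, and the documents do not support them:

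- That the duration test will be significant, or can only repeat the onset result. The probability in step 2 starts at 11%, and the test also responds to real differences on later days.
- That a significant overall test would be reported as a lasting effect. The plan does not say so.
- That the models are run without a sphericity correction. The plan is silent, so the finding is only that the handling is not specified.
- That sharing baseline and day 7 raises the error rate. Two independent tests at 0.05 give 1 - 0.95² = 9.75%. With the shared days and sphericity, simulation gives about 9%, slightly lower. The excess over 5% comes from having two tests.

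**Conclusion.** The concern holds in a limited form. The overall duration test mixes the end-of-treatment effect with persistence, so a significant result is not evidence that the effect outlasts treatment. That part rests on the design alone.

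The size rests on assumptions. At 0.5 to 0.7 SD and 20 to 50 subjects, a trial with no post-treatment effect would have a significant duration model roughly half the time at the low end and almost always at the high end. Below that range of effect or sample the rate falls, and other correlation patterns would move it. The fallback on unadjusted t-tests carries a false-positive rate of about three to four times 5%. Unspecified sphericity handling is a smaller matter, worth up to about three percentage points on the duration test. The data remain usable; what changes is the conclusion that may be drawn on a stated aim for the primary outcome.

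**What to change.** 1. Use baseline, d8, d10, d14, d21 and d35 in the overall duration test. Keep day 7 versus later days only as named contrasts describing the decline from the end of treatment.
2. State that the duration conclusion rests on the five paired contrasts of d8, d10, d14, d21 and d35 with baseline, reported with confidence intervals and Holm-adjusted p-values. State also that the overall test shows only whether some post-treatment day differs.
3. Report the Greenhouse-Geisser p-value in both repeated-measures models.

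This changes the text of the Statistical Analysis Plan and needs no new data or visits. The cost is nominal power. In an assumed example with n = 30 and an effect of 0.5 SD through day 10 that fades by day 21, the duration test goes from 82% as planned to 71% without day 7 and with the correction. Part of that loss is the day 7 effect no longer being counted as duration. Holm also lowers the power of each single-day contrast, since the smallest p-value must be below 0.01.
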